6.3 Tissue Procurement Exclusion Criteria

Subjects meeting any of the following criteria are NOT eligible for tissue procurement for the Vigil manufacturing:

1. Medical condition requiring any form of chronic systemic immunosuppressive therapy (steroid or other) except physiologic replacement doses of hydrocortisone or equivalent

(no more than 30 mg hydrocortisone or 10 mg prednisone equivalent daily) for < 30 days duration.

- Known history of other malignancy unless having undergone curative intent therapy without evidence of that disease for ≥ 3 years except cutaneous squamous cell and basal cell skin cancer, superficial bladder cancer, *in situ* cervical cancer or other *in situ* cancers are allowed if definitively resected.
- 3. Brain metastases unless treated with curative intent (gamma knife or surgical resection) **and** without evidence of progression for ≥ 2 months.
- Any documented history of autoimmune disease with exception of Type 1 diabetes on stable insulin regimen, hypothyroidism on stable dose of replacement thyroid medication, vitiligo, or asthma not requiring systemic steroids.
- 5. Known HIV or chronic Hepatitis B or C infection.
- 6. Known hypersensitivity to any temozolomide component or to dacarbazine (DTIC).
- 7. Known hypersensitivity to irinotecan or its excipients.
- 8. Known history of allergies or sensitivities to gentamicin.
- 9. History of or current evidence of any condition (including medical, psychiatric or substance abuse disorder), therapy, or laboratory abnormality that might confound the results of the study, interfere with the patient's participation for the full duration of the study, or is not in the best interest of the patient to participate, in the opinion of the treating Investigator.

6.4 Study Enrollment Inclusion Criteria

Subjects will be eligible for registration if they meet the tissue procurement inclusion criteria and all of the following study enrollment inclusion criteria:

- 1. Completed manufacture of at least 4 vials of Vigil.
- 2. Karnofsky performance status (KPS) / Lansky performance status (LS) ≥80%.
- 3. Normal organ and marrow function as defined below:

Absolute granulocyte count	≥1,000/mm³
Absolute lymphocyte count	≥400/mm³
Platelets	≥75,000/mm³
Hemoglobin	≥8.0 mg/dL
Total bilirubin	≤ institutional upper limit of normal*
AST(SGOT)/ALT(SGPT)	≤2x institutional upper limit of normal
Creatinine	<1.5 mg/dL

*documented Gilbert's syndrome may be considered after medical monitor review

- 4. Subject has recovered to CTCAE Grade 1 (except for parameters noted in Item 3, above) or better from all adverse events associated with prior therapy or surgery. Preexisting motor, sensory neurologic pathology or symptoms, or dermatologic must be recovered to CTCAE Grade 2 or better.
- 5. If female of childbearing potential, has a negative urine or serum pregnancy test. If the urine test is positive or cannot be confirmed as negative, a negative serum test will be required for study entry.
- 6. Ability to understand and the willingness to sign a written informed protocol specific consent or a parental/guardian informed consent and pediatric assent when appropriate.

6.5 Study Enrollment Exclusion Criteria

In addition to the procurement exclusion criteria, subjects will NOT be eligible for study registration and randomization if meeting any of the following additional criteria:

- 1. Any anti-neoplastic therapy between tissue procurement for Vigil manufacture and start of study therapy.
- 2. Live vaccine used for the prevention of infectious disease administered < 30 days prior to the start of study therapy.
- 3. Post-surgery complication that in the opinion of the treating investigator would interfere with the patient's study participation or make it not in the best interest of the patient to participate.

7.0 WITHDRAWAL

7.1 Discontinuation from Study Treatment

Treatment will be continued until progressive disease by RECIST 1.1. However, insofar as some patients in our early vaccine trials had increased survival despite initial, short-term volume increase. There is accumulating evidence that some subjects treated with immune system stimulating agents may appear to demonstrate progression of disease by conventional response criteria before demonstrating clinical objective responses and/or stable disease and ultimately survival benefit. It may be that enhanced inflammation within tumors initially leads to an increase in tumor size or newly visible small lesions. Over time, both the malignant and inflammatory portions of the mass may then decrease leading to overt signs of clinical improvement.

Therefore, selected subjects may be allowed to continue study therapy after investigatorassessed RECIST 1.1 progression and with agreement by the Gradalis medical monitor if the subject is determined to be deriving clinical benefit, tolerating study drug and meeting the following criteria:

- 1. Absence of symptoms and signs indicating clinically significant PD indicating disease progression.
- 2. No decline in ECOG performance status.
- 3. Absence of rapid progression of disease or of progressive tumor at critical anatomical sites (e.g., cord compression) requiring urgent alternative medical intervention.

If subsequent imaging shows an objective response or stable disease relative to baseline, treatment with study agents will continue. If subsequent imaging again shows PD, patients will be discontinued from study therapy.

Subjects will discontinue **study treatment** if any of the following occur:

- 1. Disease progression by RECIST 1.1 criteria.
- 2. The patient experiences unacceptable (≥Grade 3) toxicity felt to be related to treatment with the Vigil immunotherapy that persists for >3 weeks. Subjects would be discontinued from both Vigil and chemotherapy.
- 3. The subject experiences unacceptable (≥Grade 3) toxicity felt to be related to treatment with irinotecan/temozolomide that persists for >3 weeks. Vigil therapy may be continued in monotherapy.
- 4. Persisting Grade 3 or 4 toxicity unrelated to treatment, defined as failing to normalize within 3 weeks.
- 5. Any Grade \geq 3 allergic reactions related to Vigil.
- 6. Grade 2 autoimmune reactions unless there is evidence of clinical benefit.
- An intercurrent illness, which would in the judgment of the investigator, affects assessments of clinical status to a significant degree or requires discontinuation of study treatment.
- 8. Cancer therapy other than protocol treatment.
- 9. Non-compliant with protocol or treatment.
- 10. Subject refuses to continue treatment.

The date of and reason for discontinuation must be noted in the electronic Case Report Form (eCRF). Every effort should be made to complete the appropriate assessments.

7.2 Treatment Delay

- Treatment may be delayed no more than 3 weeks to allow recovery from toxicity.
- If ≥ one 2-week delay due to disease or infection occurs, subject status must be reviewed by sponsor.
- If subjects miss doses, the doses will be made up the following week and continue on a revised every 3-week schedule thereafter.

If Vigil administration is delayed, then irinotecan and temozolomide should concurrently be delayed.

8.0 INVESTIGATIONAL PLAN

8.1 Subject Screening and Registration

Written documentation of full, non-contingent IRB approval of the protocol and consent document must be on file before a subject can be registered. Study participation begins once written informed consent is obtained. Subjects will be assigned a study identification number upon scheduling of tissue procurement for Vigil manufacture.

No later than the date of surgery, a pre-registration packet will be submitted by the site to [contact] for medical monitor review.

One to eight weeks after tissue procurement has occurred eligibility will be reconfirmed by the study site. The Site will register the subject by sending the registration packet to [contact] for medical monitor review.

Please allow 48 hours for subject registration as the medical monitor may review the subject's source documents to ensure they meet the eligibility criteria. Once confirmed, the site will be notified of the eligibility and randomization result.

8.2 Tumor Procurement

Refer to the Study Reference Manual for instructions. Surgery for tissue procurement for Vigil manufacture must be scheduled and approved in advance.

The cumulative equivalent of a "grape" to "golf ball size" mass (~10-30 gm of prime tumor tissue / approximate 2 cm total diameter on imaging) is optimal for Vigil manufacturing. If surgeons have the option of collecting more tissue, more doses of Vigil may be prepared (up to 12 doses). Vigil manufacturing is rarely successful with small (<10 gm) tumor masses. Lesions extending into lumen (e.g., bowel) or tumor embedded in bone cannot be processed.

Once the procured tissue is received at Gradalis, Inc. samples will be processed for autologous Vigil manufacture.

8.3 Vigil Immunotherapy Manufacturing

Gradalis, Inc. will manufacture vaccine from the procured subject tumors. Gradalis, Inc. will release Vigil once all release criteria have been met and eligibility has been confirmed.

No tissue or Vigil will be given to the participant or site apart from the outlined clinical protocol.

Any excess tumor tissue, not used for Vigil manufacture will be used towards Vigil research and process development assays.

8.4 Study Treatment Administration

Treatment will be administered on an outpatient basis.

8.4.1 Schedule, Dose and Administration

	Drug	Dose	Schedule	
	Temozolomide 100 mg/m ² daily, oral		Days 1 – 5, every 21 days	
Group A	Irinotecan 50 mg/m ² daily, oral		Days 1 – 5, every 21 days	
	Vigil	1.0 x 10 ⁶ cells/injection, intradermal	Day 15, every 21 days	

Cross-Over	Drug	Dose	Schedule
Subjects	Vigil	1.0 x 10 ⁶ cells/injection, intradermal	every 21 days

Subjects will receive Vigil at 1.0×10^6 cells via intradermal injection **every 3 weeks for a minimum of 4 administrations to** a maximum of 12 administrations depending on quantity of Vigil manufactured from surgical specimens and so long as the patient is clinically stable and without disease progression.

The sites of injection for Vigil will be rotated between the right and left upper arms. If the ipsilateral axillary lymph nodes were radiated or surgically removed during prior therapy, alternative sites may be used.

	Drug	Dose	Schedule
Group B Temozolomide		100 mg/m² daily, oral	Days 1 – 5, every 21 days
	Irinotecan	50 mg/m² daily, oral	Days 1 – 5, every 21 days

Please contact the sponsor with any dose adjustment considerations.

Irinotecan Preparation

Order the injectable formulation of irinotecan from central supplier, Clinigen. Draw up 1 cycle of (five doses) into provided oral syringes and dispense to the subject with instructions to refrigerate until administration. Irinotecan may be mixed with cranberry-grape juice before administration to mask the bitter flavor and administered once daily on Days 1 through 5 of each 3-week cycle.

Temozolomide Preparation

Temozolomide capsules for 1 cycle will be obtained by the patient with administration instructions. Temozolomide may be opened and mixed in apple sauce or juice if unable to swallow whole capsules. Temozolomide is administered on Days 1 through 5 of each 3-week course and given at least 1 hour before irinotecan.

Subjects should be instructed to complete a dosing diary for the administration of oral irinotecan and oral temozolomide.

Premedications and post medications

Vigil: EMLA® may be utilized at the injection site prior to Vigil administration. Analgesics may be employed as necessary. As noted above, systemic steroids or other immunosuppressants should be avoided due to immune inhibition activity.

Temozolomide / irinotecan: Per package inserts and institutional standards. A home supply of anti-emetic (e.g. ondansetron) is highly recommended to take before temozolomide and as needed. Also, a patient supply of an anti-diarrheal medication (e.g. loperamide) should be available after irinotecan for use as needed.

The patient should be educated with a study calendar indicating days to get chemotherapy and/or Vigil as well as supportive care medications and when Vigil is given.

Vigil Immunotherapy Transfer

All manufactured Vigil will be stored in the vapor phase of liquid nitrogen until ready for use. The site will contact Gradalis, Inc. when the study agent is needed for subject administration.

Gradalis will complete a Drug Transfer and Administration Form to release the subject vaccine. The clinic will sign off on the form upon receipt of the administration.

Please reference the Study Reference Manual for preparation and handling information.

Dose Modification for Vigil Toxicity

If > Grade 2 toxicity by NCI Common Toxicity Criteria (excluding Grade 3 injection site reactions) develops related to study treatment the Vigil dose will be reduced by 50% and continued.

Dose Modifications for temozolomide and irinotecan

Dose modifications for temozolomide, and irinotecan may be necessary for subject safety and should be carried out in accordance with the Investigator's standard of practice, the package inserts, and institutional standards. Please contact the sponsor regarding any dose modifications.

If irinotecan + temozolomide is administered beyond 12 cycles, it will be administered off study and no longer provided by Gradalis.

If irinotecan + temozolomide is discontinued, Vigil may be administered every 3 weeks until all manufactured product is exhausted or when disease progression is noted.

Study Regimen Delay

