Figure 2. Low Dose Vigil Phase I Survival status. Arrow indicates subjects still alive.

Figure 3. Low Dose Vigil Phase I ELISPOT response status. Gray lines indicates time points off treatment.

Figure 4. Low Dose Vigil Phase I Ewing's Patients: ELISPOT response status. Gray lines indicates time points off treatment.

Eighty patients in total (54 females, aged 13-84 / 26 males, aged 12-76) entered into Phase I trial involving 19 solid tumor cancers. Four hundred sixty-four (464) Vigil injections were administered and no \geq Grade 3 toxic events attributed to Vigil have been observed. Dose administered ranged from 1 x 10⁶ cells/injection to 2.5 x 10⁷ cells/injection via intradermal injection once a month for a minimum of 4 months. The prolonged survival shown in Figure 5 involving predominantly advanced stage, heavily pretreated patients is greater than historical expectation (Senzer, Barve et al. 2013).

Figure 5. Long term survival by cancer type of patients entered into Vigil Phase I trial.

Moreover, correlation of survival benefit with recent follow up involving the first 30 Phase I patients to receive Vigil to yIFN ELISPOT response which measures Vigil turned on circulating immune cells (T effector cells) against autologous tumor suggests efficacy tied to predicted mechanism of Vigil (Figure 6).

Figure 6. Correlated survival and immune response and updated analysis of Vigil Phase 1 patients. 78% ELISPOT conversion rate. 55% ELISPOT (+) patients are still alive vs. 13% ELISPOT (-) are deceased. (Analysis performed on 02/27/17)

These results have recently been updated (Figure 6). Sixty-seven (67) of these Phase I patients have now undergone IFNγ ELISPOT testing. Fifty-two demonstrated change from negative at baseline (prior to Vigil treatment) to positive IFNγ ELIPSOT reactivity after Vigil (78% conversion rate). However, fifteen failed to show upregulation of circulating active effector T cells against autologous tumor induction by Vigil. Survival correlation continues to be demonstrated in this 4-year updated analysis.

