Event Term	CTC Grade	Relationship to VIGIL	Relationship to Temozolomide	Relationship to Irinotecan	Number of Subjects	Number of Events
--	--------------	--------------------------	---------------------------------	-------------------------------	--------------------------	------------------------
Platelet Count Decreased	3	Not Related	Probably Related	Probably Related	1	1
Anemia	3	Not Related	Unlikely Related	Unlikely Related	1	2
Chest Wall Pain	3	Not Related	Not Related	Not Related	1	1
Febrile Neutropenia	3	Not Related	Probably Related	Probably Related	1	1
Hypokalemia	3	Not Related	Not Related	Not Related	1	4
Neutrophil count decreased	3	Not Related	Possibly Related	Possibly Related	2	2
	3	Not Related	Probably Related	Probably Related	1	2
	4	Not Related	Probably Related	Probably Related	2	2
Platelet Count Decreased	3	Not Related	Probably Related	Probably Related	2	2
	4	Not Related	Not Related	Not Related	1	1
	4	Not Related	Probably Related	Probably Related	1	1
Pneumonitis	4	Not Related	Not Related	Not Related	1	1
Respiratory Failure	4	Not Related	Not Related	Not Related	1	1
Respiratory, thoracic and mediastinal disorders - Other, Empyema Lt. Thorax Infection	4	Not Related	Not Related	Not Related	1	1
Back Pain	5	Not Related	Not Related	Not Related	1	1
Musculoskeletal and connective tissue disorder - Other, Progressive Ewing's Sarcoma	5	Not Related	Not Related	Not Related	1	1

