increased GMCSF expression and decreased TGFB production shown to effectively modulate immunogenicity as evidenced by the correlation of IFNy-ELISPOT responsiveness with overall survival and the elicitation of the CD4+ mediated circulating antibody responses against CT47 in two of the Phase 1 Ewing's sarcoma patients. The preliminary evidence of safety, immune stimulation and clinical benefit from Vigil in patients with Ewing's sarcoma treated in the Phase I setting supports evaluation of this therapy in a larger and randomized study and at earlier stage of recurrence (first recurrence). A lower tumor burden is typically associated with greater delay in progression with other immunotherapies. Mathematical modeling supports the concept of better control of disease progression with the combined use of effective chemotherapy (e.g., temozolomide/irinotecan as second line treatment in Ewing's sarcoma) and immunotherapy (i.e., Vigil) in first relapse patient population (de Pillis, Gu et al. 2006). The utilization of the standard of care temozolomide/irinotecan regimen at investigator consensus defined dose and schedule appears to be minimally immunosuppressive and thus a reasonable option for combination with Vigil. Moreover, the temozolomide and irinotecan regimen at effective dose levels has low myelosuppressive toxicities (irinotecan 50mg/m²/dose and temozolomide 100mg/m²/dose) and may increase the tumor antigen release and surface exposure of calreticulin (part of the specific danger-signaling system) as well as reduce the frequency of CD4+ CD25+ regulatory T-cells (Kim, Kim et al. 2010). In addition, given that Ewing's sarcoma expression levels of type-1 associated chemokine ligands CXCL9, CXCL10, and CCL5 correlate with TIL expression chemokine receptors (CXCR3 and CCR5) (Berghuis, Santos et al. 2011) it is notable that temozolomide has been shown to enhance tumor matrix presentation of CXCL9 and CXCL10 in certain tumor models (Tan, Evrard et al. 2015). Temozolomide and irinotecan in combination have shown benign safety profiles without any Grade 3 treatment-related adverse events in seven combination treated Ewing's Sarcoma patients of Part 2 of CL-PTL-121. Furthermore, clinical antitumor activity was demonstrated in 4 of the 7 combination treated patients, all of whom had previously failed temozolomide and irinotecan, as evidenced by 2 partial responses, one histological CR (autopsy) and one prolonged SD currently near 1 year in duration. Thus, the combination of low dose Vigil, irinotecan and temozolomide may not only increase anti-tumor responses but also prolong time to progression and improve the of quality of life in the treatment of Ewing's sarcoma patients.

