16.3 Analysis Populations

The intent-to-treat (ITT) population will include all randomized subjects. All efficacy analyses will be completed in the ITT population.

The Safety population will include all patients who receive study treatment and patients will be analyzed according to actual treatment received. All safety analyses will be completed in the Safety population.

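### The Vigil dose-reduction rule is headed as a rule for Vigil toxicity but triggered by toxicity of any study treatment, so sites could dose the experimental arm differently

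*Protocol*

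**What the plan says.** Section 8.4.1 of the Protocol sets two dose-modification rules, one after the other. The first is headed "Dose Modification for Vigil Toxicity". It begins "If > Grade 2 toxicity by NCI Common Toxicity Criteria (excluding Grade 3 injection site reactions) develops related to study treatment the Vigil dose", so it applies to toxicity above Grade 2 and exempts Grade 3 injection site reactions, and it states that when such toxicity "develops related to study treatment the Vigil dose will be reduced by 50% and continued". The second covers temozolomide and irinotecan and leaves their adjustment to investigator practice, package inserts and institutional standards, with sponsor contact.

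Section 7.1 lists reasons for discontinuing study treatment and names the product in several of them:
- Item 3 covers irinotecan/temozolomide toxicity of Grade 3 or higher lasting more than 3 weeks. It adds "Vigil therapy may be continued in monotherapy" and mentions no reduction.
- Item 5 discontinues for any Vigil-related allergic reaction of Grade 3 or higher.

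The planned Vigil dose is 1.0 x 10⁶ cells/injection (Protocol 5.0 and 8.4.1; SAP 5.0). For Phase I, Protocol 2.0 reports: "Dose administered ranged from 1 x 10⁶ cells/injection to 2.5 x 10⁷ cells/injection".

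SAP 13.1 summarises dosing compliance by treatment group and lists exposure data. It does not mention dose reductions or their cause.

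**The concern.** The rule governs how much investigational product Group A receives, and its heading and its operative sentence point to different triggers. A site that follows the heading reduces Vigil only for toxicity it attributes to Vigil. A site that follows the sentence also reduces Vigil for Grade 3 or 4 neutropenia it attributes to the chemotherapy.

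The two readings are far apart in practice. The Protocol reports no Grade 3 or higher event attributed to Vigil in 464 Phase I injections (section 2.0), yet tabulates chemotherapy-related Grade 3 and 4 cytopenias. The narrow rule would seldom apply; the broad one would apply to a known effect of the backbone drugs.

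At stake are uniform delivery of the regimen under test and the ability to describe afterwards what was delivered. The planned analyses would not bring the matter out: the dose subgroup in Protocol 16.4.5 and SAP 8.1.5 counts doses received, not dose level.

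**Working it through.** **1. What *study treatment* covers.** Three places use it for more than Vigil:
- Section 8.4, on administration of study treatment, gives all three drugs.
- Section 7.1 lists irinotecan/temozolomide toxicity among the reasons for stopping study treatment.
- Section 16.3 says: "The Safety population will include all patients who receive study treatment and patients will be analyzed according to actual treatment received". Group B receives only chemotherapy until cross-over, so this population covers both arms only if chemotherapy counts as study treatment.

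**2. The readings side by side.**

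| Event in Group A | 8.4.1 by its heading | 8.4.1 by its sentence | 7.1 |
|---|---|---|---|
| Chemotherapy-attributed Grade 3 or 4 cytopenia, resolved within 3 weeks | Vigil unchanged | Vigil halved | No specific rule |
| Chemotherapy-attributed Grade 3 or higher, lasting more than 3 weeks | Vigil unchanged | Vigil halved | Item 3: Vigil may continue alone; no reduction mentioned |
| Vigil-attributed allergic reaction, Grade 3 or higher | Vigil halved and continued | Vigil halved and continued | Item 5: discontinue |
| Grade 3 injection site reaction | Exempt | Exempt | No specific rule |

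The first two rows turn on the trigger wording. The third is a conflict with 7.1 on either reading.

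**3. How the trigger acts on the Protocol's own data.** The table of Grade 3 to 5 events by relationship to each drug stands before section 3.0; its title is not in the available text. Sixteen rows are visible, all rated not related to Vigil. Rows rated possibly or probably related to temozolomide and irinotecan are:
- neutrophil count decreased: 3 rows (Grade 3 possibly related, 2 subjects; Grade 3 probably related, 1; Grade 4 probably related, 2);
- platelet count decreased: 3 rows (Grade 3, 1 subject; Grade 3, 2 subjects; Grade 4, 1 subject);
- "Febrile Neutropenia": 1 row (Grade 3, 1 subject).

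That makes 3 + 3 + 1 = 7 rows. A study-treatment trigger is met by 7 of 16 rows, a Vigil-attributed trigger by 0 of 16. Rows may share subjects, so the firm minimum is the largest single row, 2 subjects. No denominator is visible.

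**4. The reduced dose.** 0.5 x (1.0 x 10⁶) = 0.5 x 10⁶ cells/injection. Against the lowest reported dose the ratio is 0.5 x 10⁶ / 1 x 10⁶ = 0.5. Section 2.0 compares 1 x 10⁷ with 2.5 x 10⁷ and describes a small cohort at 1 x 10⁶. Nothing lower is reported in the available text, some of which was removed.

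**5. Sample size.** Events = 4(z for 0.9762 + z for 0.90)² / (ln 0.45)² = 4(1.981 + 1.282)² / 0.638 = 66.8, so 67, as the plan states (power 90.1%). The wording defect changes no stated sample-size figure.

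**The case against.** The strongest reply is that context already settles the meaning. The heading names Vigil toxicity, a parallel heading follows for the chemotherapy, and the only exemption is a Vigil effect. Section 8.4.1 also asks sites to contact the sponsor about dose adjustments, which makes divergent dosing less likely. Section 7.1 item 3 is a stopping rule for persistent toxicity, so its silence on reduction is not a strict contradiction. All of this stands, and it means the literal reading cannot be presented as the only one. It does not remove the mismatch: the operative sentence uses the broader term, whereas 7.1 shows that the Protocol can name the product when it means one.

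Three stronger readings are tempting, and the documents support none of them.
- *A reader might infer that a calculable share of Group A would be reduced*, by dividing the table's counts by the seven combination patients in section 3.0. The table's population is not visible and its rows may overlap. Those seven had already failed both chemotherapy drugs, whereas this trial enrols after one prior line and permits growth factors (section 8.5).
- *A reader might infer that the treatment effect would be diluted.* No data are given below 1 x 10⁶. The dose comparison reported, at higher doses, showed similar results, and 12 of 12 evaluable patients at 1 x 10⁶ converted on ELISPOT. Reduction follows an event rather than starting at the first injection, and an ITT comparison tests a regimen together with its modification rules. If half the dose kept full effect, power would stay at 90%; any other figure needs both an assumed share and an assumed loss.
- *A reader might infer that section 3.0 is wrong to say* "without any Grade 3 treatment-related adverse events in seven combination treated Ewing's Sarcoma patients of Part 2 of CL-PTL-121". The table appears to conflict with it, but that holds only if both describe the same patients.

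**Conclusion.** The rule is wrong as written. Its heading and trigger disagree on whether chemotherapy toxicity changes the Vigil dose, and its instruction to halve and continue conflicts with 7.1 item 5 for Vigil-related allergic reactions of Grade 3 or higher. The practical gap is 7 of 16 visible table rows on one reading against none on the other, counting possible and probable relationship as related.

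The reduced dose is half the lowest dose in the available text. That follows from the 50% step on either reading, so clarifying the trigger does not remove it. The size and direction of any effect on PFS cannot be determined from the documents. The point rests on the inconsistent dosing instruction, not on a projected hazard ratio or loss of power.

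Attribution will remain a judgement even under a clear trigger, because section 14.3 lists cytopenias among the expected effects of Vigil.

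**What to change.** - **Protocol 8.4.1 and 7.1.** The sponsor should reconcile the heading and trigger sentence of the Vigil rule with 7.1 items 3 and 5, and name in the trigger the product or products whose attributed toxicity changes the Vigil dose. Which product, dose or rule is right is for the sponsor and its clinical advisers; none is proposed here.
- **SAP 13.1.** Add the number of Group A subjects with a reduced Vigil dose, by attributed cause where the eCRF records it. Protocol 14.4 already has dose reductions recorded. Section 14.2 records relationship to treatment without saying that it is per product, so this should be confirmed.
- **Separate query.** Establish whether the Grade 3 to 5 event table and the safety statement in Protocol 3.0, repeated in SAP 2.0, describe the same patients, and reconcile them if so.

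The cost is a wording amendment, with the IRB approval that section 11.5 requires, and one line in the exposure summary. No sample-size change is needed. No new data are needed unless the eCRF lacks per-product attribution.

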Reference the Study Reference Manual for preparation and handling information.

Vigil concentrate: 1.0×10^6 cells per injection in a volume of 1mL.

Route of administration: Intradermal injection

Storage and Shipping

Frozen, unopened vials are stored in the vapor phase of Liquid Nitrogen below -150° C at Gradalis. Each Vigil concentrate will be shipped individually in a portable liquid nitrogen tank. This shipping container will be able to sustain temperature fluctuations for up to 7 days. This will enable sufficient time to reach the different clinical site pharmacies.

Study medications are not expected to pose significant occupational safety risks to investigational staff under normal conditions of use and administration. However, precautions

should be taken to avoid direct contact with study medication. Biosafety Level 1 practices shall be employed with this study medication. Reference the Study Reference Manual.

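### For a Vigil-related allergic reaction that is systemic Grade 3, or Grade 4, protocol 8.4.1 says halve Vigil and continue while 7.1 item 5 says stop, and no visible text says which rule prevails

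*Protocol*

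**What the plan says.** Protocol section 8.4.1, under Dose Modification for Vigil Toxicity, sets a rule for toxicity above Grade 2: "excluding Grade 3 injection site reactions) develops related to study treatment the Vigil dose will be reduced by 50% and continued". The Grade 3 injection site reaction is the only exception named. Allergic reactions are not mentioned, and there is no reference to section 7.1.

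Protocol section 7.1 introduces its stopping list with "Subjects will discontinue study treatment if any of the following occur". Two items matter here.

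- Item 5 covers any "allergic reactions related to Vigil" of Grade 3 or higher, with no condition on duration.
- Item 2 covers "toxicity felt to be related to treatment with the Vigil immunotherapy that persists for >3 weeks", again at Grade 3 or higher. Here persistence is part of the criterion.

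The controls around dosing are these.

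- Section 8.4.1 tells sites "Please contact the sponsor with any dose adjustment considerations".
- On supply, 8.4.1 adds "The site will contact Gradalis, Inc. when the study agent is needed for subject administration" and "Gradalis will complete a Drug Transfer and Administration Form to release the subject vaccine".
- Section 13.1 states "Each Vigil concentrate will be shipped individually in a portable liquid nitrogen tank".
- Section 14.5 requires serious adverse events to reach the sponsor within 24 hours.

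**The concern.** A treating physician faced with a severe systemic allergic reaction to Vigil would naturally turn to the part of the protocol on dose modification for Vigil toxicity. It says to continue at half dose. The instruction to stop is in another section, and 8.4.1 does not point to it. Both rules are worded as mandatory.

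What is at stake is the safety of an individual patient: re-exposure at half dose after an event that section 7.1 treats as a reason to stop. Treatment is outpatient (section 8.4) and patients may be as young as 2 years (section 6.2). The inconsistency does not touch the primary comparison.

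**Working it through.** **1. Do the rules cover the same grades?** Above Grade 2 and Grade 3 or higher are the same set. Within it, a choice about further dosing arises only for Grades 3 and 4.

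**2. Where do they collide?** Setting the rules side by side for Vigil-related events:

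| Event | 8.4.1 | 7.1 | Conflict |
|---|---|---|---|
| Allergic, Grade 3, confined to the injection site | May be excluded from the reduction rule | Item 5: stop | None if the exclusion applies |
| Allergic, Grade 3, systemic | Halve and continue | Item 5: stop | Yes |
| Allergic, Grade 4 | Halve and continue | Item 5: stop | Yes |
| Other, Grade 3 or higher, not lasting beyond 3 weeks | Halve and continue (Grade 3 injection site reactions excluded) | Item 2 not met | No |
| Other, Grade 3 or higher, lasting beyond 3 weeks | Halve first (same exclusion) | Item 2: stop | No, the rules follow in sequence |

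Item 2 can be read together with 8.4.1 because its duration condition leaves room for an initial reduction. Item 5 leaves no such room. In the two conflict rows the instructions are half of 1.0 x 10^6 cells, that is 0.5 x 10^6 cells per injection, against none.

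**3. Is there a tie-breaker?** Protocol sections 7.2, 8.5, 8.7, 10, 14 and 15 and the SAP contain no precedence rule and no cross-reference between the two sections. The nearest text is the instruction to contact the sponsor, which says whom to ask and not what the answer is. One limit applies: parts of the documents are not visible, and the heading Study Regimen Delay, which follows the dose rules in 8.4.1, has no visible text under it.

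**4. How often could it arise?** The plan gives no rate for allergic reactions, so only a ceiling can be worked out. Section 2.0 reports 80 Phase I patients, 464 injections and no event of Grade 3 or higher attributed to Vigil. With zero events in n patients, the exact one-sided 95% upper bound is 1 - 0.05^(1/n).

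- n = 80: 1 - 0.05^(1/80) = 0.0368, or 3.7%. Applied to the 57 Group A subjects this is 2.1. If all of Group B also crossed over, 114 subjects would receive Vigil and the figure is 4.2.
- n = 85, adding the 5 Vigil patients of CL-PTL-121 Part 1 (section 2.4), who also had none: 1 - 0.05^(1/85) = 0.0346, or 3.5%. This gives 2.0 of 57 or 3.9 of 114.

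These bounds cover all Vigil-attributed toxicity of Grade 3 or higher. Allergic reactions are a subset, and those in the conflict rows a smaller one.

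**The case against.** The strongest reply is that the rules act at different stages. Section 7.1 ends treatment, 8.4.1 sets the dose for a patient who remains on Vigil, and a discontinued patient has no dose to halve. Item 5 is also the specific rule and 8.4.1 the general one. Section 8.4.1 itself gives Vigil only while the patient is clinically stable, and the sponsor controls release. This largely stands as an account of what would happen. It does not remove the inconsistency, because the protocol does not state the order of precedence and none of the supply or reporting controls supplies it.

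Four stronger readings are tempting, and the documents do not support them.

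- *That every Grade 3 or higher Vigil-related allergic reaction is caught.* Vigil is given intradermally, and section 14.3 lists urticaria or rash and pruritus among local reactions at the injection site. A Grade 3 reaction confined to that site may be excluded from 8.4.1, leaving item 5 alone.
- *That naming one exception in 8.4.1 rules out all others.* That exception only limits when the dose is lowered. It says nothing about overriding stop rules set elsewhere.
- *That patients would in fact be re-dosed.* The sensible reading and the sponsor's control of release both point the other way.
- *That about 2 of 57 cases should be expected.* That figure is an upper bound on a wider class of events. The figure for 114 further assumes universal crossover, although sections 10.0 and 10.1 require progression, adequate performance status and laboratory values, and sponsor approval.

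**Conclusion.** The inconsistency is real and minor. As written, 8.4.1 and 7.1 item 5 give opposite mandatory instructions for a Vigil-related allergic reaction that is systemic Grade 3, or Grade 4, and no visible text says which governs. It does not extend to Vigil-related toxicity in general.

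The 3.7% bound assumes that all 80 Phase I patients were dosed and that their risk is comparable to the risk in this trial. The absence of a precedence rule is established only for the visible text. There is no effect on power, alpha or sample size, and any effect on exposure or discontinuation counts would be negligible. The reason to act is that a safety stop for an individual patient should not depend on interpretation.

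**What to change.** Add one sentence to the Vigil dose-modification rule in section 8.4.1:

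*This reduction rule does not apply to events meeting a Section 7.1 discontinuation criterion, including any Grade >=3 allergic reaction related to Vigil; Section 7.1 prevails.*

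This can be done by amendment or clarification letter. It adds no procedures, patients or analyses, and the SAP needs no change.
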